12.10.6. Safety Figures

Safety: Figures					
No.	Population	IDSL / Example Shell	Title	Programming Notes	Deliverable [Priority]
Adverse Events					
3.1.	Safety	AE10	Plot of Common ($\geq 10\%$) Adverse Events and Relative Risk (Part A only) by Randomised Treatment	IDSL	IA SAC [1], SAC [1]
3.2.	Safety	AE10	Plot of Common ($\geq 10\%$) Adverse Events and Relative Risk (Parts A, B and Follow-up) by Randomised Treatment	IDSL	IA SAC [1], SAC [1]
3.3.	Safety	AE10	Plot of Common ($\geq 10\%$) Adverse Events and Relative Risk (Parts A, B and Follow-up) by Period Treatment	IDSL	IA SAC [1], SAC [1]
Laboratory					
3.4.	Safety	LIVER14	Scatter Plot of Maximum Versus Baseline for ALT (Parts A, B and Follow-up) by Randomised Treatment	IDSL	IA SAC [1], SAC [1]
3.5.	Safety	LIVER14	Scatter Plot of Maximum Versus Period Baseline for ALT (Parts A, B and Follow-up) by Period Treatment	IDSL	IA SAC [1], SAC [1]
3.6.	Safety	LIVER9	Scatter Plot of Maximum ALT Versus Maximum Total Bilirubin ALT (Parts A, B and Follow-up) by Randomised Treatment	IDSL	IA SAC [1], SAC [1]
3.7.	Safety	LIVER9	Scatter Plot of Maximum ALT Versus Maximum Total Bilirubin (Parts A, B and Follow-up) by Period Treatment	IDSL	IA SAC [1], SAC [1]

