5. CONSIDERATIONS FOR DATA ANALYSES AND DATA HANDLING CONVENTIONS

5.1. Study Treatment & Sub-group Display Descriptors

One subject was randomised to a BID regimen before the protocol was amended. Per instructions in the protocol, data will be summarised in tables and figures by treatment (GSK2982772 60mg or Placebo) irrespective of dosing regimen received (BID or TID). Data will be listed per treatment and dosing regimen received (BID or TID). Some key safety endpoints will be summarised by both randomised treatment and period treatment, details are provided in [Appendix 9](#).

Should a participant receive the wrong medication at any point during the study in error, that participant will be treated as having received GSK2982772 60mg TID for the duration of the study.

Randomised Treatment Group Descriptions					
RandAll NG		Data Displays for Reporting			
Code	Description	Description in tables/non-PK figures	Order in TF	Description in Listings/PK figures	Order in Listing
A	GSK2982772 60mg BID (Double-blind)	GSK2982772 60mg	2	GSK2982772 60mg BID	3
C	GSK2982772 60mg TID (Double-blind)	GSK2982772 60mg	2	GSK2982772 60mg TID	4
P	Placebo BID (Double-blind)	Placebo	1	Placebo BID	1
Q	Placebo TID (Double-blind)	Placebo	1	Placebo TID	2

Period Treatment Group Descriptions					
RandAll NG		Data Displays for Reporting			
Code	Description	Description in tables	Order in TF	Description in Listings	Order in Listing
A	GSK2982772 60mg BID (Double-blind)	GSK2982772 60mg	2	GSK2982772 60mg DB BID	3
B	GSK2982772 60mg BID (Open-label)	GSK2982772 60mg	2	GSK2982772 60mg OL BID	5
C	GSK2982772 60mg TID (Double-blind)	GSK2982772 60mg	2	GSK2982772 60mg DB TID	4
D	GSK2982772 60mg TID (Open-label)	GSK2982772 60mg	2	GSK2982772 60mg OL TID	6
P	Placebo BID (Double-blind)	Placebo	1	Placebo DB BID	1
Q	Placebo TID (Double-blind)	Placebo	1	Placebo DB TID	2

Treatment comparisons will be displayed as follows using the descriptors as specified:

- GSK2982772 60mg vs Placebo.

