7.2.1. Clinical Laboratory Summary Measures

Clinical Laboratory data will be summarised in tables and figures by the following:

- Parts A, B and Follow-up by randomised treatment;
- Parts A, B and Follow-up by period treatment (i.e. treatment participant actually received).

Clinical Laboratory data will be presented in data listings by the following:

- Parts A and B and follow-up by period treatment (i.e. treatment participant actually received).

Table 4 Overview of Planned Clinical Laboratory Analyses

Endpoint / Parameter/ Display Type	Absolute			Change from BL		
	Summary		Individual	Summary		Individual
	T	F	L	T	F	L
Chemistry						
Chemistry Results				Y		
Chemistry Lipids Results ^[1]				Y ^[2]		
Worst Case Chemistry Results Relative to PCI Criteria Post-Baseline Relative to Baseline	Y					
Worst Case Lipids Results Relative to NR Criteria Post-Baseline Relative to Baseline ^[1]	Y					
Lipids Outside of the Normal Range ^[1]			Y			
Hematology						
Hematology Results				Y		
Worst Case Hematology Results Relative to PCI Criteria Post-Baseline Relative to Baseline	Y					

Endpoint / Parameter/ Display Type	Absolute			Change from BL		
	Summary		Individual	Summary		Individual
	T	F	L	T	F	L
Urinalysis						
Urine Concentration				Y		
Worst Case Urinalysis Results (Discrete or Character Values) Post-Baseline Relative to Baseline	Y					
Hepatobiliary (Liver)						
Liver Monitoring/Stopping Event Reporting	Y					
Hepatobiliary Laboratory Abnormalities	Y					
Medical Conditions for Subjects with Liver Stopping Events			Y			
Substance Use for Subjects with Liver Stopping Events			Y			
Scatter Plot of Maximum Versus Baseline for ALT		Y				
Scatter Plot of Maximum ALT Versus Maximum Total Bilirubin		Y				
All Laboratory ^[3]						
All Laboratory Data for Subjects with Any Value of PCI			Y			
Laboratory Data with Character Results			Y			

NOTES:

- T = Table, F = Figures, L = Listings, Y = Yes display generated, PCI = Potential Clinical Importance
- Summary = Represents TF related to any summaries (i.e. descriptive statistics) of the observed raw data.
- Individual = Represents L related to any displays of individual participant observed raw data.

1: Lipids parameters = LDL Cholesterol, HDL Cholesterol, Total Cholesterol, Triglycerides and Cholesterol/HDL ratio

2: Percentage changes from baseline.

3: Chemistry, Hematology and Urinalysis will be considered.

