12.6. Appendix 6: Derived and Transformed Data

12.6.1. General

Multiple Measurements at One Analysis Time Point

 • Mean of the measurements will be calculated and used in any derivation of summary statistics but if listed, all data will be presented. • Participants having both High and Low values for Normal Ranges at any post-baseline visit for safety parameters will be counted in both the High and Low categories of “Any visit post-baseline” row of related summary tables. This will also be applicable to relevant Potential Clinical Importance (PCI) summary tables.
Study Day

 • Calculated as the number of days from First Dose Date: 
 • Ref Date = Missing → Study Day = Missing • Ref Date < First Dose Date → Study Day = Ref Date – First Dose Date • Ref Date ≥ First Dose Date → Study Day = Ref Date – (First Dose Date) + 1

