3.21.	Safety	AE16	Summary of Serious Adverse Events by System Organ Class and Preferred Term (Number of Subjects and Occurrences) (Parts A, B and Follow-up) by Period Treatment	FDAAA, EudraCT	IA SAC [1], SAC [1]
3.22.	Safety	AE1	Summary of Adverse Events Leading to Permanent Discontinuation of Study Treatment or Withdrawal from Study (Part A only) by Randomised Treatment	IDSL	IA SAC [1], SAC [1]
3.23.	Safety	AE1	Summary of Adverse Events Leading to Permanent Discontinuation of Study Treatment or Withdrawal from Study (Parts A, B and Follow-up) by Randomised Treatment	IDSL	IA SAC [1], SAC [1]
3.24.	Safety	AE1	Summary of Adverse Events Leading to Permanent Discontinuation of Study Treatment or Withdrawal from Study (Parts A, B and Follow-up) by Period Treatment	IDSL	IA SAC [1], SAC [1]
Laboratory: Chemistry					
3.25.	Safety	LB1	Summary of Chemistry Changes from Baseline (Parts A, B and Follow-up) by Randomised Treatment	ICH E3	IA SAC [1], SAC [1]
3.26.	Safety	LB1	Summary of Chemistry Changes from Period Baseline (Parts A, B and Follow-up) by Period Treatment	ICH E3	IA SAC [1], SAC [1]
3.27.	Safety	LB1	Summary of Lipids Percentage Changes from Baseline (Parts A, B and Follow-up) by Randomised Treatment	Lipids parameters = LDL Cholesterol, HDL Cholesterol, Total Cholesterol, Triglycerides and Cholesterol/HDL ratio	IA SAC [1], SAC [1]

Safety: Tables					
No.	Population	IDSL / Example Shell	Title	Programming Notes	Deliverable [Priority]
3.28.	Safety	LB1	Summary of Lipids Percentage Changes from Period Baseline (Parts A, B and Follow-up) by Period Treatment	Lipids parameters = LDL Cholesterol, HDL Cholesterol, Total Cholesterol Triglycerides and Cholesterol/HDL ratio	IA SAC[1], SAC [1]
3.29.	Safety	LB17	Summary of Worst Case Chemistry Results by PCI Criteria Post-Baseline Relative to Baseline (Parts A, B and Follow-up) by Randomised Treatment	ICH E3 (i.e. treatment emergent)	IA SAC [1], SAC [1]
3.30.	Safety	LB17	Summary of Worst Case Chemistry Results by PCI Criteria Post-Baseline Relative to Period Baseline (Parts A, B and Follow-up) by Period Treatment	ICH E3 (i.e. treatment emergent)	IA SAC [1], SAC [1]
3.31.	Safety	LB17	Summary of Worst Case Lipids Results by NR Criteria Post-Baseline Relative to Baseline (Parts A, B and Follow-up) by Randomised Treatment	Lipids parameters = LDL Cholesterol, HDL Cholesterol, Total Cholesterol Triglycerides and Cholesterol/HDL ratio	IA SAC [1], SAC [1]

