3.44.	Safety	LIVER10	Summary of Hepatobiliary Laboratory Abnormalities (Parts A, B and Follow-up) by Period Treatment	IDSL	IA SAC [1], SAC [1]
ECGs					
3.45.	Safety	EG1	Summary of ECG Findings (Parts A, B and Follow-up) by Randomised Treatment	IDSL	IA SAC [1], SAC [1]
3.46.	Safety	EG1	Summary of ECG Findings (Parts A, B and Follow-up) by Period Treatment	IDSL	IA SAC [1], SAC [1]
3.47.	Safety	EG10	Summary of Maximum QTc Values Post-Baseline Relative to Baseline by Category (Parts A, B and Follow-up) by Randomised Treatment	IDSL	IA SAC [1], SAC [1]
3.48.	Safety	EG10	Summary of Maximum QTc Values Post-Baseline Relative to Screening by Category (Parts A, B and Follow-up) by Randomised Treatment	Change relative to average of screening triplicates	SAC[1]
3.49.	Safety	EG10	Summary of Maximum QTc Values Post-Baseline Relative to Period Baseline by Category (Parts A, B and Follow-up) by Period Treatment	IDSL	IA SAC [1], SAC [1]
3.50.	Safety	EG2	Summary of Change from Baseline in ECG Values (Parts A, B and Follow-up) by Randomised Treatment	IDSL	IA SAC [1], SAC [1]
3.51.	Safety	EG2	Summary of Change from Screening in ECG Values (Parts A, B and Follow-up) by Randomised Treatment	Change relative to average of screening triplicates	SAC [1]
3.52.	Safety	EG2	Summary of Change from Period Baseline in ECG Values (Parts A, B and Follow-up) by Period Treatment	IDSL	IA SAC [1], SAC [1]
3.53.	Safety	EG11	Summary of Maximum Increase in QTc Values Post-Baseline Relative to Baseline by Category (Parts A, B and Follow-up) by Randomised Treatment	IDSL	IA SAC [1], SAC [1]

Safety: Tables					
No.	Population	IDSL / Example Shell	Title	Programming Notes	Deliverable [Priority]
3.54.	Safety	EG11	Summary of Maximum Increase in QTc Values Post-Baseline Relative to Screening by Category (Parts A, B and Follow-up) by Randomised Treatment	Change relative to average of screening triplicates	SAC [1]
3.55.	Safety	EG11	Summary of Maximum Increase in QTc Values Post-Baseline Relative to Period Baseline by Category (Parts A, B and Follow-up) by Period Treatment	IDSL	IA SAC [1], SAC [1]
Vital Signs					
3.56.	Safety	VS1	Summary of Change from Baseline in Vital Signs (Parts A, B and Follow-up) by Randomised Treatment	ICH E3	IA SAC [1], SAC [1]
3.57.	Safety	VS1	Summary of Change from Period Baseline in Vital Signs (Parts A, B and Follow-up) by Period Treatment	ICH E3	IA SAC [1], SAC [1]

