3.58.	Safety	VS7	Summary of Worst Case Vital Signs Results by PCI Criteria Post-Baseline Relative to Baseline (Parts A, B and Follow-up) by Randomised Treatment	IDSL	IA SAC [1], SAC [1]
3.59.	Safety	VS7	Summary of Worst Case Vital Signs Results by PCI Criteria Post-Baseline Relative to Period Baseline (Parts A, B and Follow-up) by Period Treatment	IDSL	IA SAC [1], SAC [1]

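### Worst-case laboratory, QTc and vital-sign tables and Figure 3.2 count open-label drug time under Placebo, and no Part A-only worst-case table by randomised arm is listed

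*SAP*

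**What the plan says.** SAP section 2.3 gives 42 days of randomised double-blind treatment (Part A), then 42 days of open-label GSK2982772 for everyone who completes Part A (Part B), then 28 days of follow-up. The randomisation is 2:1 with about 36 participants. Section 2.2 names adverse events, clinical laboratory values, vital signs and ECG as the primary endpoints. Section 2.4 plans no formal hypothesis for them.

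Section 7.1.1 summarises adverse events in three cuts: Part A by randomised treatment, all parts by randomised treatment, and all parts by period treatment. Sections 7.2.1 (laboratory) and 7.3.1 (ECG, vital signs) have only the last two; the randomised cut is "Parts A, B and Follow-up by randomised treatment".

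The display list in section 12.10 follows this pattern:

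- Figure 3.1 plots the relative risk of common adverse events for Part A. Figure 3.2 plots "Adverse Events and Relative Risk (Parts A, B and Follow-up) by Randomised Treatment". Figure 3.3 does so by period treatment.
- Table 3.29 is "Summary of Worst Case Chemistry Results by PCI Criteria Post-Baseline Relative to Baseline (Parts A, B and Follow-up) by Randomised Treatment". Table 3.53 is "Summary of Maximum Increase in QTc Values Post-Baseline Relative to Baseline by Category (Parts A, B and Follow-up) by Randomised Treatment". Table 3.58 is "Summary of Worst Case Vital Signs Results by PCI Criteria Post-Baseline Relative to Baseline (Parts A, B and Follow-up) by Randomised Treatment". Tables 3.35 (haematology) and 3.47 (maximum QTc) have the same form.
- Period-treatment versions of these tables exist (3.30, 3.36, 3.49, 3.55, 3.59). The two QTc tables relative to screening, 3.48 and 3.54, have none.

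In section 5.1 the randomised placebo codes appear in tables as Placebo. In the period-treatment descriptors, the double-blind and open-label drug codes share one table column.

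**The concern.** In Part B, a comparison by randomised arm sets drug against drug. A relative risk, or a count of people whose worst value crossed a limit, that runs from Day 1 to follow-up therefore mixes the randomised contrast with a period that has none. Read as drug against placebo, it pulls a real difference towards no difference.

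For adverse events a Part A version stands beside the pooled one. For outlying laboratory, QTc and vital-sign values none is listed. A worst-case table is where an infrequent signal in a few people would be looked for, and mean changes by visit can miss it. These are named primary endpoints in a trial whose only randomised comparison lasts six weeks.

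**Working it through.** The SAP gives no event rates and no stated figure to reproduce, so the rates below are assumptions. Design inputs are from section 2.3: 24 and 12 participants (2:1 of 36), 42 + 42 + 28 days. All calculations assume no dropout.

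**Share of placebo-arm treatment time on drug.** 42 / 84 = 50%.

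**Figure 3.2.** Let p be the background risk per 42 days, with daily hazard h = −ln(1 − p)/42. The hazard is constant and doubled on drug.

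- Part A: (1 − e^(−84h)) / (1 − e^(−42h)). At p = 0.10: 0.190 / 0.100 = 1.90.
- Parts A and B: (1 − e^(−168h)) / (1 − e^(−126h)) = 0.344 / 0.271 = 1.27.
- With follow-up at the background hazard: (1 − e^(−196h)) / (1 − e^(−154h)) = 0.388 / 0.320 = 1.21.
- With follow-up still at the doubled hazard: (1 − e^(−224h)) / (1 − e^(−182h)) = 0.430 / 0.367 = 1.17.
- Range for Part A against Parts A and B: 1.95 to 1.30 at p = 0.05, and 1.70 to 1.16 at p = 0.30.

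**Randomised-arm worst-case tables.** The schedule in section 12.2.1 gives three post-baseline visits in Part A (Days 15, 29, 43, the last pre-dose) and three in Part B (Days 57, 71, 85) for vital signs, ECG, haematology and chemistry. The follow-up visit is left out here. Let f be the chance of a flag at a placebo visit and 2f at a drug visit.

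- Part A, independent visits: [1 − (1 − 2f)³] / [1 − (1 − f)³]. At f = 0.05: 0.271 / 0.143 = 1.90.
- Parts A and B: [1 − (1 − 2f)⁶] / [1 − (1 − f)³(1 − 2f)³] = 0.469 / 0.375 = 1.25.
- Range: 1.96 to 1.30 at f = 0.02, and 1.80 to 1.18 at f = 0.10.
- With a Gaussian latent within-person correlation of 0.5 and f = 0.05: 1.84 to 1.22.
- With fully correlated flags: 2f/f = 2.0 falls to 2f/2f = 1.0.

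The dilution therefore does not depend on independent visits.

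**Period-treatment worst-case tables, no drug effect.** Suppose one maximum is taken per person across both periods, which the SAP does not say. The drug column then holds 24 people with six visits and 12 with three; the placebo column holds 12 with three. The ratio is {24[1 − (1 − f)⁶] + 12[1 − (1 − f)³]}/36 divided by [1 − (1 − f)³]. At f = 0.05 it is 0.224 / 0.143 = 1.57 (1.63 at f = 0.02, 1.49 at f = 0.10). It is 1.38 at latent correlation 0.5, and 1.0 if flags are fully correlated.

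**Figure 3.3, no drug effect.** Days per participant on drug are (24 × 84 + 12 × 42)/36 = 70, against 42 on placebo, a ratio of 1.67. If the figure uses participant proportions, the relative risk is {[24(1 − e^(−84h)) + 12(1 − e^(−42h))]/36} / p. At p = 0.10 this is 0.160 / 0.100 = 1.60 (1.63 at p = 0.05, 1.47 at p = 0.30). Follow-up is excluded, because no rule says which column takes it.

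**Date rules.** Section 12.4.1 counts the treatment start date as Pre-Treatment, while 12.4.2 counts an adverse event on that date as On-Treatment. Section 12.4.1 also places all of Day 43 in Part A, although footnote 10 of the schedule has the morning dose given at site that day, when Part B begins. Taking Days 2 to 43 as Part A and Day 43 as a drug day, the ratio at p = 0.10 is (1 − e^(−84h)) / (1 − e^(−43h)) = 1.86, against 1.90.

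**The case against.** The pooled displays are one openly titled cut among several. For adverse events, Figure 3.1 and eight Part A tables already give the randomised contrast, so Figure 3.2 is at worst a redundant plot with a poor label. The by-visit change tables (3.25, 3.33, 3.50, 3.56) give the contrast for mean values. The primary objective concerns safety over 12 weeks with no test, so a 12-week summary by randomised sequence is legitimate. All of this stands, and a reader should not infer that the plan lacks any randomised safety comparison.

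The shells are not shown (section 12.11), so visit rows in the worst-case tables cannot be ruled out. They would give flag frequencies at Days 15, 29 and 43 by arm, but not how many people were flagged at least once in Part A.

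Three stronger readings are tempting and not supported:

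- Section 12.6.1 might be taken to fix the tables' window at all post-baseline visits. Its sentence on "Participants having both High and Low values for Normal Ranges at any post-baseline visit for safety parameters" only says that such people count in both categories. The pooling is shown by the table titles and by 7.2.1 and 7.3.1.
- The period-treatment tables might be said to be biased against the drug. Section 5.2 resets the period baseline at Day 43. If each period is counted separately, three visits face three and the artefact largely goes.
- The date rules might be thought to distort Part A. Under a constant hazard they barely move it. Day 1 and Day 43 laboratory, ECG and vital-sign assessments are pre-dose, so the boundaries suit those assessments; the loose end concerns adverse events.

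Precision is also poor. With 24 and 12 participants and risks of 19% and 10%, a log-scale 95% interval around 1.90 runs from 0.29 to 12.5; around the pooled 1.27 it runs from 0.43 to 3.7. Dilution in expectation is small against that noise. This limits what any safety table here can show, but it does not justify listing only the diluted one.

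**Conclusion.** The concern holds for Figure 3.2 and for the randomised-arm worst-case and maximum tables. Half of the planned treatment time shown there as Placebo is on drug, and no Part A-only version of the worst-case tables is listed. Under a doubled hazard or flag rate, a ratio near 1.9 in Part A shows as about 1.25 when Parts A and B are pooled. The exact size rests on assumed rates; the direction does not.

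The period-treatment tables do not fill the gap, because double-blind and open-label drug share a column. Whether they or Figure 3.3 also show a spurious excess (up to about 1.6) depends on counting rules that the SAP leaves open. Adverse events and mean changes are already protected. No error rate is affected; what suffers is interpretation of the primary safety objective. It should be fixed before the final displays are run.

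**What to change.** 1. In 7.2.1, 7.3.1 and 12.10.5, add Part A-only worst-case or maximum tables by randomised treatment for chemistry, haematology, QTc and vital signs, using post-baseline visits up to Day 43 pre-dose.
2. In Figure 3.2, drop the relative risk, or label the arm Placebo then GSK2982772. Keep Figure 3.1 as the relative-risk display.
3. Show exposure-adjusted rates with Figure 3.3. State which column takes follow-up adverse events, and how a participant with two periods is counted in the period-treatment tables.
4. Minor: reconcile the Day 1 and Day 43 boundaries in 12.4.1 with 12.4.2 for adverse events, and define the end of Part A for participants without a Day 43 visit.

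All of this uses data already collected. The cost is SAP wording, a few more tables and a longer display list.

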Study Duration and Dosing	
 Each participant will participate in the study for approximately 20 weeks. This includes a screening period up to 30 days, an 84-day (12 week) treatment period, and a 28-day follow-up period after the last dose. Within 30 days of the screening visit (defined as day of consent signing), eligible participants enter a 2-part treatment phase as follows with study treatment starting on study day 1: 
 Part A: Approximately 36 participants are randomly assigned to receive either GSK2982772 60 mg three times daily (TID) or placebo TID for 42 days (6 weeks) in a 2:1 ratio. Part B: All participants who complete Part A move on to receive open label treatment of GSK2982772 60 mg TID for an additional 42 days (6 weeks). Treatment duration is a total of 84 days (12 weeks) inclusive of Parts A and B. Participants are followed-up for 28 days (4 weeks) after the last dose in Part B. Prior to amendment 01 being effective in each country, participants were randomly assigned to receive either: 
 Part A: GSK2982772 60 mg two times daily (BID) or placebo BID for 42 days (6 weeks) in a 2:1 ratio. Part B: Open label treatment for all participants who have completed Part A of GSK2982772 60 mg BID for an additional 42 days (6 weeks). 																															
Time & Events	
 Refer to Appendix 2: Schedule of Activities. During the 84-day (12 week) treatment period, participants attend the clinical for visits on Days 1, 15, 29, 43, 57, 71 and 85. At specific visits, participants must not take treatment prior to their scheduled treatment. On Days 8, 22, 36, 50, 64 and 78 participants were to be contacted by telephone and asked about their general health. Participants are given a diary card at every visit and asked to record daily study 																															

Overview of Study Design and Key Features	
	medication, concomitant medication and adverse events.

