7.1.1. Adverse Event Summary Measures

AE data will be summarised in tables and figures by the following:

- Part A by randomised treatment;
- Parts A, B and follow-up by randomised treatment;
- Parts A, B and follow-up by period treatment (i.e. treatment participant actually received).

AE data will be presented in data listings by the following:

- Parts A, B and follow-up by period treatment (i.e. treatment participant actually received).

Table 3 Overview of Planned Adverse Event Analyses

Endpoint / Parameter/ Display Type	Absolute		
	Summary		Individual
	T	F	L
Adverse Events (AEs)			
All AE by Maximum Intensity by SOC and PT	Y		
All Drug-Related AEs by Maximum Intensity by SOC and PT	Y		
Common ($\geq 10\%$) AEs / Drug-Related AEs by Overall Frequency	Y	Y ^[1]	
Common ($\geq 10\%$) Non-serious AEs by SOC and PT (Number of Subjects and Occurrences)	Y		
All AEs	Y		Y
Subject Numbers for Individual AEs			Y
Relationship Between AE SOCs, PT & Verbatim Text			Y
Serious and Other Significant AEs			
Serious AEs by SOC and PT (Number of Subjects and Occurrences)	Y		
Fatal Serious AEs			Y
Non-Fatal Serious AEs			Y
AEs Leading to Permanent Discontinuation of Study Treatment or Withdrawal from Study	Y		Y
Reasons for Considering as a Serious AE			Y
Possible Suicidality-Related AE (PSRAE)			Y

NOTES:

- T = Table, F = Figures, L = Listings, Y = Yes display generated, SOC = System Organ Class, PT = Preferred Term.
 - Summary = Represents TF related to any summaries (i.e. descriptive statistics) of the observed raw data.
 - Individual = Represents L related to any displays of individual participant observed raw data.
- 1: Plot of common AEs and relative risk will be generated.

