			Day 1	Day 8 (±3)	Day 15 (±3)	Day 22 (±3)	Day 29 (±3)	Day 36 (±3)	Day 43 (±3) (week 6)	Day 50 (±3)	Day 57 (±3)	Day 64 (±3)	Day 71 (±3)	Day 78 (±3)			Day 85 (+2) (week 12)
Urine pregnancy test (WCBP only) ¹²			X ⁴		X		X		X ⁴		X		X		X	X	X
Haematology, chemistry, urinalysis	X		X ⁴		X		X ¹³		X ⁴		X ¹³		X ¹³		X	X	X
Faecal calprotectin ¹⁴		X	X		X		X		X		X		X		X	X	
Blood sample for exploratory biomarkers and TE ¹⁵			X ⁴						X ⁴						X	X	
PK blood samples GSK2982772 ¹⁶			X						X ⁴						X	X	
Biopsies for PK, inflammatory biomarkers, mRNA, TE & pathway marker analysis		X-----X ⁷							X ⁴						X	X ⁸	
Pharmacogenetic sample (PGx) ¹⁷			X														

Footnotes:

1. Full medical history (includes past and current conditions, medication history, substance usage, and family history of premature CV disease).
2. Full physical exam (includes height/weight at screening, height not measured at later time points).
3. Triplicate ECG to be performed at screening only and if stopping criteria are met.
4. Pre-dose.
5. Any SAEs assessed as related to study participation (e.g., protocol-mandated procedures, invasive tests, or change in existing therapy) or related to a GSK product will be recorded from the time a participant consents to participate in the study up to and including any follow-up. AEs will be collected from the start of Study Treatment until the follow-up contact.
6. PRO assessments should be conducted before any tests, procedures or assessments to avoid influencing the participants' perception.

7. Sigmoidoscopy may be performed at any time during the screening window as an additional visit (if required) up to Day -7 in order for central reading confirmation of Mayo Score for inclusion. If a shorter window is required (e.g., within Day -3 to Day -7), this will be permitted as long as it has been confirmed with the sponsor and central reader that results of the Mayo endoscopy score will be available before end of screening window. Histological disease (e.g., UCEIS, MRS and Geboes Index) along with Mayo score assessments will also be completed.

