12.4. Appendix 4: Study Phases and Treatment Emergent Adverse Events

12.4.1. Study Phases

Treatment phases will be defined for Part A and Part B of the study. Therefore, assessments and events will be classified according to the time of occurrence relative to study treatment start date and the Day 43 visit.

Study Phase	Definition
Pre-Treatment	Date ≤ Study Treatment Start Date
On-Treatment	Study Treatment Start Date < Date ≤ Study Treatment Stop Date
On-Treatment (Part A)	Study Treatment Start Date < Date ≤ Day 43 Visit Date
On-Treatment (Part B)	Day 43 Visit Date < Date ≤ Study Treatment Stop Date
Post-Treatment	Date > Study Treatment Stop Date

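### Figure 3.3 sets an AE relative risk on columns of unequal observation time (about 98 or 70 days against 42), and Sections 12.4.1 and 12.4.2 disagree on AEs with onset on the treatment start date

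*SAP*

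**What the plan says.** Section 7.1.1 plans three AE views: Part A by randomised treatment, all parts by randomised treatment, and "Parts A, B and follow-up by period treatment (i.e. treatment participant actually received". A note to Table 3 adds: "Plot of common AEs and relative risk will be generated". Section 12.10.6 turns this into three figures on the AE10 shell. Figure 3.1 shows common "Adverse Events and Relative Risk (Part A only) by Randomised Treatment", Figure 3.2 covers all parts by randomised treatment, and Figure 3.3 shows common "Adverse Events and Relative Risk (Parts A, B and Follow-up) by Period Treatment".

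Section 2.3 gives the design: "All participants who complete Part A move on to receive open label treatment of GSK2982772 60 mg TID for an additional 42 days", followed by 28 days of follow-up after the last dose. AE collection is set in footnote 5 of Section 12.2.1: "AEs will be collected from the start of Study Treatment until the follow-up contact".

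The period-treatment table in Section 5.1 lists open-label codes such as "GSK2982772 60mg TID (Open-label") under the same table label as double-blind drug. The only other label is Placebo, and there is no follow-up or off-treatment column. No exposure adjustment is stated for any AE display.

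On dates, Section 12.4.1 says that "assessments and events will be classified according to the time of occurrence relative to study treatment start date and the Day 43 visit". Its pre-treatment phase includes the treatment start date, and its Part A phase begins strictly after that date. Section 12.4.2 makes an AE on-treatment if onset is on or after the treatment start date. Section 12.7.2.1 moves some partial onset dates to that date and calls those events on-treatment.

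**The concern.** AEs are a primary endpoint. A relative risk invites the reader to take 1 as no effect, and in Figure 3.3 that reading fails. One column is watched for longer than the other, the later time is all in the drug column, and some participants sit in both. A departure from 1 could come from observation time, from a change in AE risk over the study, or from the drug, and the figure cannot separate these.

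The date rules matter because the fair comparison rests on them. Section 12.4.2 has no split between Part A and Part B, so the Part A displays (Figure 3.1 and Tables 3.1, 3.4, 3.7, 3.10, 3.13, 3.16, 3.19 and 3.22) need the Part A window of Section 12.4.1. That window leaves out the day of the first dose.

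**Working it through.** The SAP gives no person-time or AE rate of its own to reproduce.

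**Inputs from the SAP.** About 36 participants at 2:1, hence 24 drug and 12 placebo; Part A 42 days; Part B 42 days, all on drug; follow-up 28 days (Section 2.3).

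**Assumptions.** Everyone completes. Follow-up is charged to the last treatment, or left out as the alternative. The AE10 ratio is a crude ratio of proportions; the shell is not shown.

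**Column time.**
- Drug with follow-up: (24 × 112 + 12 × 70)/36 = 3528/36 = 98 days.
- Drug without follow-up: (24 × 84 + 12 × 42)/36 = 2520/36 = 70 days.
- Placebo: 504/12 = 42 days.
- Time ratio: 98/42 = 2.33, or 70/42 = 1.67.

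**Ratio with no drug effect.** Let r be the assumed six-week risk, h = −ln(1 − r)/42 the daily hazard in Part A, f·h the hazard after Day 42, and L the days counted after Day 42 (70 with follow-up, 42 without). Then

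ratio = {[24(1 − exp(−42h − fhL)) + 12(1 − exp(−fhL))]/36} / r.

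Example, r = 10%, f = 1, L = 70: the risks are 1 − 0.9^(112/42) = 0.245 and 1 − 0.9^(70/42) = 0.161. The drug column is (24 × 0.245 + 12 × 0.161)/36 = 0.217, and 0.217/0.10 = 2.17. For L = 42: (24 × 0.19 + 12 × 0.10)/36 = 0.16, and the ratio is 1.60.

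| Later hazard ÷ Part A hazard (f) | With follow-up, r = 5 / 10 / 20 / 30% | Without follow-up, r = 5 / 10 / 20 / 30% |
|---|---|---|
| 1 | 2.25 / 2.17 / 2.01 / 1.86 | 1.63 / 1.60 / 1.53 / 1.47 |
| 0.5 | 1.48 / 1.45 / 1.40 / 1.35 | 1.16 / 1.15 / 1.12 / 1.10 |
| 0.25 | 1.08 / 1.07 / 1.05 / 1.03 | 0.91 / 0.91 / 0.90 / 0.89 |

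At r = 10% the ratio equals 1 when f is 0.207 (with follow-up) or 0.345 (without). With 10, 20 or 30% dropout spread evenly over Part A, the value at r = 10%, f = 1, L = 70 becomes 2.07, 1.96 or 1.86.

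**Would a rate ratio cure it?** Not if pooled. At r = 10% and L = 70, the ratio of first events per time at risk with no drug effect is 1.00 for f = 1, but 0.65 for f = 0.5 and 0.47 for f = 0.25.

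**Treatment start date, side by side.**
- Section 12.4.1: covers events; start date is pre-treatment; Part A begins the day after.
- Section 12.4.2: AE with onset on the start date is on-treatment; no split by part.
- Section 12.7.2.1: if the first of the month falls before treatment start, an onset with a missing day is set to the start date and counted on-treatment.

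An AE on that date is therefore on-treatment under two sections and outside Part A under the only section that defines Part A.

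**The case against.** The strongest objection is that the figure is descriptive. Section 2.4 plans no formal hypotheses for safety, three AE views are given on purpose, Figure 3.1 supplies the balanced comparison, and the title of Figure 3.3 names both the parts covered and period treatment. This stands and limits the consequence, but it does not give the ratio a usable reference value.

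The size is also conditional. The AE10 shell is not shown, no rule assigns follow-up AEs to a column, and the SAP gives no AE rates. The values above are ratios of expected proportions and ignore the selection of terms at 10% or more. Noise is large: a 10% term has no placebo event among 12 with probability 0.9^12 = 0.28, and 8/36 against 1/12 gives a ratio of 2.67 with a 95% interval of about 0.37 to 19. All of this stands.

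A reader might infer that Figure 3.3 must overstate harm, or that participants average 98 days on drug. The documents support neither. The ratio can fall below 1 if AE risk drops enough after Day 42, and 28 of the 98 days are off drug.

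On the treatment start date, Section 12.4.2 can be read as the specific rule for AEs, with Section 12.4.1 suited to pre-dose Day 1 assessments. That settles the on-treatment flag but not membership of Part A. A reader might also infer that the conflict biases drug against placebo, or that the Day 43 rule is a second contradiction. It treats both arms alike, and the Day 43 rule is a single rule.

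**Conclusion.** Two rules are wrong as written and should be fixed, though neither undermines the planned Part A comparison.

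First, the relative risk in Figure 3.3 has no interpretable null value. The unequal column time (98 or 70 days against 42) follows from the design, given 24:12 and full completion. The resulting shift does not: at a 10% six-week risk it ranges from 2.17 under constant hazard with follow-up to 0.91 when the later hazard is a quarter and follow-up is left out. Neither size nor direction is fixed, and all of it assumes a crude ratio. The same unequal columns appear without a ratio in the period-treatment AE Tables 3.3, 3.6, 3.9, 3.12, 3.15, 3.18, 3.21 and 3.24. Figure 3.2 compares randomised groups over the same period and does not share the time imbalance.

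Second, taken literally, Section 12.4.1 removes first-dose-day AEs, and partial-date AEs imputed to that day, from Figure 3.1 and the eight Part A tables. The number affected cannot be derived from the SAP.

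**What to change.** - Keep the relative risk for the randomised Part A comparison in Figure 3.1.
- In Figure 3.3, drop the ratio and show person-time per column. Footnote that the columns differ in observation time, share participants and are not a randomised comparison.
- Put the same person-time and footnote on Tables 3.3, 3.6, 3.9, 3.12, 3.15, 3.18, 3.21 and 3.24.
- If rates are wanted, show exposure-adjusted incidence separately for Part A, Part B and follow-up. Do not form a ratio of pooled rates, because that also assumes a constant hazard.
- In Section 12.4.1, define Part A for AEs to include onset on the treatment start date, in line with Section 12.4.2. Keep the existing rule for pre-dose Day 1 assessments.
- The Day 43 date rule needs at most a footnote.

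The cost is SAP wording, one ratio removed, person-time and a shared footnote on nine displays, and one AE date rule applied to Figure 3.1 and the eight Part A tables. The downside is that a pooled whole-study ratio by treatment actually received is no longer shown.
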